**Figure 1 Part-1 study design**

### Part-2: Multiple-dose part

A total of 20 subjects will be enrolled in Part-2 in two cohorts and randomized to fosmanogepix or placebo. This part will have a randomized, double-blind, parallel multiple-dose design. All subjects in Cohort 3 and Cohort 4 will receive a 3-hour IV infusion twice daily (BID) 12 hours apart on Day 1. In Cohort 3, subjects will receive the maintenance dose via a 3-hour IV infusion, once daily (QD) from Day 2 to Day 7. In Cohort 4, subjects will receive the maintenance dose via a 3-hour IV infusion, QD on Day 2 and Day 3, and switch to oral administration QD from Day 4 to Day 7. Eight subjects in each cohort will be randomized to fosmanogepix and two subjects will be randomized to placebo.

The total duration of participation in Part-2 is up to 70 days, comprising a screening period of up to 28 days, a treatment and observation duration of 22 days (7 days of dosing and a

15-day full PK profile after the last dose), and a follow-up call 28 – 35 days after the last dosing.

**Figure 2 Part-2 study design**

## 3.2 Study endpoints

### 3.2.1 Primary endpoints

The primary endpoints are the plasma PK parameters for manogepix including:

- Part-1 (Single-dose):
  - $C_{max}$ ,  $T_{max}$ ,  $AUC_{0-24h}$ ,  $AUC_{last}$ ,  $AUC_{inf}$
  - CL (or CL/F for Cohort 1),  $V_{ss}$  (or  $V_z/F$  for Cohort 1),  $t_{1/2}$ , F as permitted by data.
- Part-2 (Multiple-dose):
  - $C_{max}$ ,  $T_{max}$ ,  $AUC_{tau}$  on Day 7
  - CL (or CL/F for Cohort 4),  $V_{ss}$  (or  $V_z/F$  for Cohort 4),  $t_{1/2}$ , F after last dose administration on Day 7 as permitted by data
  - $C_{trough}$  (Trough concentration) on Day 1 (second dose), Day 2, Day 3, Day 6, Day 7, Day 8 (24 hours after last dose), as permitted by data.

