6.1.1.2 PART-2: Multiple dose

In PART-2, subjects will be enrolled in two cohorts and randomized to fosmanogepix or placebo:

- All subjects (Cohort 3 and Cohort 4) will receive a 3-hour IV infusion (1,000 mg fosmanogepix or placebo, BID) 12 hours (± 10 minutes) apart on Day 1.
- In Cohort 3, subjects will receive the maintenance dose of 600 mg fosmanogepix or placebo, 3-hour IV infusion QD from Day 2 to Day 7.
- In Cohort 4, subjects will receive the maintenance dose of 600 mg fosmanogepix or placebo, 3-hour IV infusion, QD on Day 2 and Day 3, and switch to oral administration of 800 mg fosmanogepix or placebo QD from Day 4 to Day 7.

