**Table 2 Plasma PK parameters for Part-2: Multiple-dose**

Parameter	Analyte	Definition	Method of determination
$AUC_{tau}$	Manogepix/ fosmanogepix*	Area under the plasma concentration-time profile from time zero to the time of the end of the dosing interval (tau), where tau = 24 hours	Linear/log trapezoidal method.
$C_{max}$	Manogepix / fosmanogepix*	Maximum plasma concentration	Observed directly from data.
$T_{max}$	Manogepix / fosmanogepix*	Time for $C_{max}$	Observed directly from data as time of first occurrence.

Parameter	Analyte	Definition	Method of determination
$t_{1/2}^*$	Manogepix	Terminal elimination half-life	$\text{Log}_e(2)/k_{el}$ , where $k_{el}$ is the terminal phase rate constant calculated by a linear regression of the log-linear concentration-time curve. Only those data points judged to describe the terminal log-linear decline will be used in the regression.
$CL^*$ (Cohort 3 only)	Manogepix	Clearance	$\text{Dose}/AUC_{\tau}$ .
$CL/F^*$ (Cohort 4 only)	Manogepix	Apparent clearance	$\text{Dose}/AUC_{\tau}$ .
$V_{ss}^*$ (Cohort 3 only)	Manogepix	Volume of distribution at steady state	$CL \times MRT$ , where MRT is the mean residence time calculated as $[AUMC_{\tau} + \tau(AUC_{inf} - AUC_{\tau})] / AUC_{\tau} - (DOF/2)$ , where $AUMC_{\tau}$ is the area under the moment curve from time 0 until the end of the dosing interval ( $\tau$ ), and DOF is the duration of the IV infusion dose.
$V_z/F^*$ (Cohort 4 only)	Manogepix	Apparent volume of distribution	$\text{Dose}/(AUC_{\tau} \times k_{el})$ .
$C_{\text{trough}}$	Manogepix	Pre-dose concentration	Observed directly from data obtained on Day 7 and Day 8 (24 hours after last dose) # .
F	Manogepix	Absolute bioavailability	$AUC_{\tau,po}(\text{dose normalized}) (\text{mean } AUC_{\tau} \text{ in Cohort 4}) / AUC_{\tau,iv}(\text{dose normalized}) (\text{mean } AUC_{\tau} \text{ in Cohort 3})$

\* As data permit.

# Other pre-dose concentrations will be collected on Day 1 (second dose), Day 2, Day 3, and Day 6.

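### Part-2 absolute bioavailability is taken from a Day 7 profile that still contains earlier IV doses, so under linear PK it is biased towards 600/800 = 0.75 by an amount that depends on the half-life

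*SAP*

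**What the plan says.** SAP 3.2.1 includes, among the Part-2 primary endpoints for manogepix, "F after last dose administration on Day 7 as permitted by data". SAP Table 2 defines this parameter as "Absolute bioavailability": mean AUCtau in Cohort 4 over mean AUCtau in Cohort 3, each dose-normalized, "where tau = 24 hours". Protocol Table 7 gives the same formula. Both abbreviation lists describe AUCtau after oral dosing as a steady-state area.

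The regimen is in protocol 6.1.1.2. On Day 1 all Part-2 subjects "will receive a 3-hour IV infusion (1,000 mg fosmanogepix or placebo, BID"). Cohort 4 then receives "600 mg fosmanogepix or placebo, 3-hour IV infusion, QD on Day 2 and Day 3", followed by a "switch to oral administration of 800 mg fosmanogepix or placebo QD from Day 4 to Day 7". Cohort 3 stays on 600 mg IV QD to Day 7. SAP 3.1 describes the same sequence.

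Neither document corrects the Day 7 area for the earlier IV doses, or asks for a steady-state check before F is computed. The protocol's PK sampling schedule has no sample on Day 4 or Day 5, so drug remaining at the switch is not measured directly. In Part-2, CL (Cohort 3) and CL/F (Cohort 4) are Dose/AUCtau, and Vz/F in Cohort 4 is Dose/(AUCtau × kel). Part-1 F is different: it is the ratio of dose-normalized single-dose AUCinf, Cohort 1 over Cohort 2.

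**The concern.** Absolute bioavailability should compare exposure from oral doses with exposure from IV doses. On Day 7 the Cohort 4 profile is a mixture of four oral doses and the remains of four IV doses. The formula divides the whole area by the 800 mg oral dose. The IV part says nothing about absorption; what it contributes to the ratio is fixed by the two doses, 600 and 800 mg.

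F, CL, CL/F and Vz/F are all primary endpoints. Part-1 F and Part-2 F would carry the same name but estimate different things. A gap between them could arise from arithmetic alone and be read as a change in absorption on repeated dosing.

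**Working it through.** The documents state no value for F, so there is no planned figure to reproduce. The check is by superposition.

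**Inputs from the documents**
- IV doses common to both cohorts: 1,000, 1,000, 600 and 600 mg at 0, 12, 24 and 48 h (protocol 6.1.1.2 and 6.1.1.3).
- Then 600 mg IV (Cohort 3) or 800 mg oral (Cohort 4) at 72, 96, 120 and 144 h.
- The Day 7 window is 144–168 h.
- PK is stated to be linear for oral 100–1,000 mg and IV 10–1,000 mg (protocol 4.3.1).

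**Assumptions**
- Half-life 12–84 h. The documents give no value. Sampling to 240 h and 360 h and the loading regimen suggest a half-life of days, but do not establish it.
- One compartment, 3-h infusions, oral absorption rate 1/h.
- Dose-normalized, which is not defined, means division by the Day 7 dose.

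**Formula.** Let R be the Day 7 AUCtau left from the four common IV doses, and A the Day 7 AUCtau per absorbed mg from the last four doses. Then

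F_est = [(R + 800·F·A)/800] / [(R + 600·A)/600] = w × 0.75 + (1 − w) × F, with w = R/(R + 600·A).

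**Hand check at 48 h** (bolus input, clearance set to 1). A dose given h hours before the start of the Day 7 window contributes, per mg, 2^(−h/48) × (1 − 2^(−24/48)), and 1 − 2^(−0.5) = 0.2929.
- R = 0.2929 × (1,000 × 0.1250 + 1,000 × 0.1487 + 600 × 0.1768 + 600 × 0.2500) = 0.2929 × 529.7 = 155.1
- A = 0.2929 × (0.3536 + 0.5000 + 0.7071 + 1) = 0.750, so 600·A = 450.0
- w = 155.1/605.1 = 0.256
- True F 0.90: 0.256 × 0.75 + 0.744 × 0.90 = 0.862

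**Results with 3-h infusions and first-order absorption**

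| Assumed half-life | w | F_est, true F 0.60 | F_est, true F 0.90 | F_est, true F 1.00 | IV residue in Cohort 4 AUCtau (F 0.90) | CL/F error, Cohort 4 (F 0.90) | CL error, Cohort 3 |
|---|---|---|---|---|---|---|---|
| 12 h | 0.005 | 0.60 | 0.90 | 1.00 | under 1% | about 0% | about 0% |
| 24 h | 0.08 | 0.61 | 0.89 | 0.98 | 7% | about 0% | −2% |
| 48 h | 0.26 | 0.64 | 0.86 | 0.94 | 23% | +3.5% | −1% |
| 72 h | 0.36 | 0.66 | 0.85 | 0.91 | 32% | +14% | +7% |
| 84 h | 0.39 | 0.66 | 0.84 | 0.90 | 35% | +20% | +13% |

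The CL/F errors combine two effects: residual IV drug, which raises AUCtau, and oral accumulation that is not complete by Day 7, which lowers it. Vz/F has the same relative error if kel is right. The Cohort 3 column shows the departure from steady state alone.

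**Part-1 for comparison.** A single-dose AUCinf ratio has no carry-over and returns the true F under linear PK.

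**Can the Day 7 dose be isolated?** Take AUC_D7 = AUCinf after the Day 7 dose − Cpre/kel. In the one-compartment model this recovers F exactly, but it is a difference of large areas: in Cohort 3, Cpre/kel is about 2.5 times the Day 7 dose's own AUC at 48 h and 3.6 times at 72 h. If kel in that term is 10% too low at 48 h, AUC_D7 becomes 1 − 2.5 × (1/0.9 − 1) = 0.72 of its true value and CL is 38% too high. If kel is 10% too high, AUC_D7 becomes 1 + 2.5 × (1 − 1/1.1) = 1.23 and CL is 18% too low. With an assumed two-compartment profile (distribution half-life 8 h carrying half the initial concentration, terminal half-life 48 h), it recovers F well (0.905 for 0.90) but puts Cohort 3 CL 13% too high, where the planned Dose/AUCtau is off by −1%.

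**The case against.** Several points on the other side have weight.

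- **The size is not known.** It rests on a half-life that the documents do not give. At 12 h the bias disappears. This stands: the direction is firm, the magnitude is not.
- **Sampling error is larger.** With eight active subjects per cohort and an assumed between-subject CV of 20–30%, the relative standard error of the ratio is √(2 × CV²/8), or 10–15%. The bias at true F 0.90 is about 4% at 48 h and 6% at 72 h. This also stands, but the bias is systematic and a relabelling avoids reporting it as F.
- **Nothing is tested, and Part-1 supplies a clean F.** True, and this is why the fix is easy and the grade moderate.
- **The plan may handle it elsewhere.** The endpoint is conditional on the data, and protocol 9.3.1.2 refers PK parameters to a separate PK analysis plan that is not among these documents. But the AUCtau formula returns a number whatever the carry-over, and the conditional wording names no criterion for withholding it.

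Two stronger readings are tempting and not supported. A reader might infer that Part-2 F lands near 0.75 whatever the truth. It does not: at 48 h about 74% of the weight is on true F, so the estimate still moves with F. A reader might also infer that the formula would create a false Chinese/non-Chinese difference. Protocol 4.3.2 chooses the regimen to match the one used in non-Chinese subjects. If the same formula was used there, the same pull applies to both; the documents do not show how F was computed in those studies.

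**Conclusion.** The concern holds in a limited form. Under the protocol's own linearity statement, and with normalization by the Day 7 doses, the Part-2 quantity labelled absolute bioavailability is a weighted mean of true F and 0.75. It reads too low when true F is above 0.75, too high when below, and is right only at 0.75. For assumed half-lives of 48–84 h the weight on 0.75 is about 0.26–0.39, and a true F of 0.90 is reported as 0.86–0.84. At 24 h the shift is about 0.01, and at 12 h it is nil.

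Cohort 4 CL/F and Vz/F use the same area, and Cohort 3 CL assumes steady state on Day 7. It might seem to follow that these should be recomputed from an isolated Day 7 dose. The calculations do not support that: the replacement can be further from the truth than the planned value.

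This should be fixed before analysis because a primary result would otherwise carry the wrong name. It does not undermine the Part-2 exposure data or the Part-1 estimate.

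**What to change.** 1. In SAP 3.2.1 and Table 2, and in protocol Tables 1, 3 and 7, rename the Part-2 ratio *Day 7 dose-normalized exposure ratio, oral after IV lead-in vs IV*. State that the divisors are the Day 7 doses.
2. Take absolute bioavailability from Part-1 only (single-dose AUCinf, Cohort 1 over Cohort 2).
3. Keep the planned CL, CL/F and Vz/F. Add a footnote that Dose/AUCtau assumes steady state on Day 7 and that in Cohort 4 the area includes residual IV exposure.
4. Optionally add, for F only and as a sensitivity analysis, the ratio based on AUC_D7 = AUCinf after the Day 7 dose − Cpre/kel, under the kel reliability rules of SAP 8.2. State that it assumes linear PK, is sensitive to error in kel and is only approximate with multi-compartment disposition. Do not use AUC_D7 to replace CL or CL/F.

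Cost: wording in both documents, with no new sample, visit or subject. Part-2 would no longer yield its own primary absolute F. Because a primary endpoint definition changes, protocol section 9 calls for a matching amendment if the change counts as major.

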### 3.2.2 Secondary endpoints

The secondary endpoints are:

- Incidence of adverse events (AEs) / serious adverse events (SAEs), clinical safety laboratory tests, vital signs, 12-lead electrocardiogram (ECGs)
- Plasma PK parameters for fosmanogepix including:
  - Part-1 (Single-dose):  $C_{\max}$ ,  $T_{\max}$ ,  $AUC_{0-24h}$ ,  $AUC_{\text{last}}$
  - Part-2 (Multiple-dose):  $C_{\max}$ ,  $T_{\max}$ ,  $AUC_{\text{tau}}$  on Day 7
- Plasma PK parameters for manogepix:
  - Part-1 (Single-dose): Fraction unbound ( $f_u$ ).

## 4 GENERAL STATISTICAL CONSIDERATIONS

Summary outputs will be presented by cohort and treatment as described below:

- Part-1: Oral low dose (Oral 400 mg), Oral high dose (Oral 800 mg), IV low dose (IV 600 mg), IV high dose (IV 1000 mg), Placebo (pooled cohort 1 and cohort 2)
- Part-2: IV only, IV and oral, Placebo (pooled cohort 3 and cohort 4).

Data from Part-1 and Part-2 will be summarized in separate tables and figures.

No formal hypothesis testing will be performed. Continuous data, unless otherwise specified, will be described using descriptive statistics (n, mean, standard deviation [SD], median, minimum, and maximum). Categorical data will be described using the subject count and percentage in each category. Non-zero percentages will be rounded to one decimal place, except 100%, which will be displayed without any decimal places. For the summary statistics of all numerical variables unless otherwise specified, minimum and maximum will be displayed to the same level of precision as reported, up to a maximum of three decimal places. Mean and median will be displayed to one level of precision greater than the data collected, up to a maximum of three decimal places. SD will be displayed to two levels of precision greater than the data collected, up to a maximum of three decimal places.

When count data are presented, the percentage will be suppressed when the count is zero, to draw attention to the non-zero counts. A row denoted 'Missing' will be included in count tabulations where specified in the table shells, to account for dropouts and missing values. The denominator for all percentages will be the number of subjects in the analysis set of interest, unless otherwise specified.

All data will be displayed in listings sorted by cohort, treatment, and subject ID – if applicable, screen failure subjects will be displayed in separately.

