4.1.1 PART-1: Single-dose part

A total of 32 subjects will be enrolled in PART-1 in two cohorts and randomized to fosmanogepix (with a low dose and a high dose in each cohort, administered in parallel) or placebo. This part will have a randomized, double-blind, parallel single-dose design. In each cohort, subjects will receive fosmanogepix or placebo by either oral administration (Cohort 1) or as a 3-hour IV infusion (Cohort 2). Six subjects in each cohort will be randomized to a low dose of fosmanogepix, six subjects will be randomized to a high dose of fosmanogepix, and four subjects will be randomized to placebo. A minimum of 3 days is required between last subject being dosed in Cohort 1 and first subject being dosed in Cohort 2.

The total duration of participation in PART-1 is up to 64 days, comprising a screening period of up to 28 days, a total treatment and observation duration of 11 days (1 day of dosing and a 10-day full PK profile after dosing), and a follow-up call 28 – 35 days after dosing.

Eligible subjects will be admitted to the clinical site on Day –1. The treatment and observation period will comprise admission with baseline assessments on Day –1, an in-clinic stay for 5 days from Day 1 to Day 5, and two outpatient visits on Day 7 and Day 11 (see the [Schedule of assessments](#)).

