6.3 Assignment to study drug

All subjects signing the ICF will be assigned a subject number in the Electronic Data Capture (EDC). On Day 1 prior to the first study drug administration, eligible subjects will be randomized.

In PART-1, 32 subjects (16 in Cohort 1, then 16 in Cohort 2) will be randomized in a 3:3:2 ratio to FMGX low-dose, FMGX high-dose, or Placebo. In PART-2, 20 subjects (10 in Cohort 3 and 10 in Cohort 4) will be randomized in a 4:1 ratio to FMGX or Placebo.

Assignment to a specific treatment arm will be controlled by the Medidata Randomization and Trial Supply Management (RTSM) system, integrated with RAVE EDC.

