9.3.2 Safety analyses

All safety analyses will be performed using the Safety analysis set. The data from PART-1 and PART 2 of the study will be analyzed and reported separately. The safety analyses will be presented in tabular and/or graphical format, and summarized descriptively by cohort and treatment group. Data from subjects on placebo will be pooled together for PART-2 (Cohort 3 and Cohort 4) analysis.

Adverse events, ECGs, vital signs, and safety laboratory data will be reviewed during the study to evaluate the safety of subjects.

Physical examination information collected during the study, will be considered source data and will not be reported, except any untoward findings during the active collection period which meet the definition of an AE. Data collected at Screening that are used for inclusion/exclusion criteria, such as medical history, laboratory data, ECGs, and vital signs, as well as demographic data will be reported as stated above.

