## 11 CHANGES IN THE PLANNED ANALYSIS

To harmonize the AESIs across fosmanogepix studies, the list of AESIs and the criteria for their identification have been updated. *Nausea* and *Vomiting* have been added, while

---

*Embryofetal toxicity* has been removed. The terms used to identify these AESIs are provided in Section 9.1.3 and are consistent with project reference documents.

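### Part-1 placebo is shown as one mixed-route column of 8 in the SAP, so neither the oral nor the IV arms are tabulated beside their own cohort's placebo group (minor; secondary safety display only)

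*SAP*

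**What the plan says.** Protocol 9.3.2 has the safety data "summarized descriptively by cohort and treatment group". It names one exception: "Data from subjects on placebo will be pooled together for PART-2 (Cohort 3 and Cohort 4) analysis". It says nothing about pooling placebo in PART-1.

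SAP Section 4 says that summaries are by cohort and treatment, then lists the Part-1 groups: four active groups, each tied to one route and dose, and one placebo group, "Placebo (pooled cohort 1 and cohort 2"). The same section pools Part-2 placebo and has all data listed by cohort, treatment and subject.

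The two Part-1 placebo groups differ in route. Protocol Table 5 gives Cohort 1 a single oral placebo dose and Cohort 2 a 3-hour placebo infusion. Protocol 4.1.1 states that in each cohort "four subjects will be randomized to placebo", and requires at least 3 days between the last dosing in Cohort 1 and the first in Cohort 2. Under Protocol 6.3, "32 subjects (16 in Cohort 1, then 16 in Cohort 2) will be randomized in a 3:3:2 ratio".

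The opening of Protocol Section 9 lets the SAP modify the protocol's outline. It asks for an amendment only for major changes to the primary endpoint definitions or their analyses. SAP Section 11, which records changes to the planned analysis, covers the AESIs only: "the list of AESIs and the criteria for their identification have been updated".

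**The concern.** The protocol's distinction between the two parts has a rationale. In Part-2 every subject receives infusions on Days 1 to 3, so the placebo subjects of Cohorts 3 and 4 share much of their experience. In Part-1 they share no route at all. The SAP removes the distinction without giving a reason.

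Safety is a secondary objective, and these tables are its main display. A reader of a Part-1 table compares each active column with the placebo column. With the pooled column, half of that comparator comes from the other route and an earlier or later dosing period.

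This matters most where the row label does not reveal the route:

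- the any-TEAE row and general preferred terms;
- laboratory summaries. The Day 1 sample (Protocol 1.3, PART-1 footnote g) is taken 3 hours after dosing or start of infusion, with a 30-minute window. That is about the end of infusion in Cohort 2, but 3 hours after a tablet in Cohort 1;
- vital signs and ECG. The concern is weaker here, because Day 11 is the only scheduled post-dose time in Part-1 (footnote l). Unscheduled and early-discontinuation readings can still enter the minimum and maximum values.

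**Working it through.** **1. Reproduce the Part-1 allocation.** Inputs: 16 subjects per cohort and ratio 3:3:2 (Protocol 6.3).

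- Low dose: 16 × 3/8 = 6. High dose: 16 × 3/8 = 6. Placebo: 16 × 2/8 = 4.
- Two cohorts: 2 × 16 = 32. This agrees with Protocol 4.1.1.
- Part-1 placebo is therefore 4 oral + 4 IV, which the SAP shows as 8.

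For comparison, Part-2 placebo is 10 × 1/5 = 2 per cohort, pooled to 4.

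**2. Set the texts side by side.**

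| Point | Protocol | SAP |
|---|---|---|
| Part-1 placebo | By cohort and treatment group; no pooling stated (9.3.2) | One pooled column (Section 4) |
| Part-2 placebo | Pooled (9.3.2) | Pooled (Section 4) |
| Listed as a change | – | No; Section 11 covers AESIs only |

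**3. Effect on a displayed rate.** With equal group sizes, the expected pooled rate is the plain average of the two routes:

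pooled = (4 × p_IV + 4 × p_oral) / 8

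The documents give no placebo event rates, so the values below are assumptions.

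| Assumed IV placebo rate | Assumed oral placebo rate | Pooled column |
|---|---|---|
| 25% | 0% | 12.5% |
| 50% | 0% | 25% |
| 50% | 25% | 37.5% |
| 25% | 25% | 25% |

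If the event occurs only with infusion, the pooled column shows half the IV background rate and gives the oral arms a background they do not have. If the two routes share the same rate, pooling does no harm. The same averaging applies to a mean laboratory change when all 8 subjects have values.

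**4. What pooling gains.** The one-sided 95% upper limit for 0 events in n subjects is 1 − 0.05^(1/n):

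- n = 4: 1 − 0.05^(1/4) = 52.7%
- n = 8: 1 − 0.05^(1/8) = 31.2%

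The larger denominator is a real gain in precision, but it applies to a mixed-route rate.

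**The case against.** The strongest case for leaving the SAP alone has four parts.

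- **The change is permitted.** Protocol Section 9 gives the SAP this latitude, and the synopsis asks for safety by cohort and dose level only where appropriate. This stands: no protocol amendment is needed. It does not explain why the change is missing from Section 11.
- **Little is lost.** A reader might infer that the randomised control is destroyed. The documents do not support that. Allocation within each cohort is unchanged, and only the summary columns are merged. With 4 placebo subjects per cohort, the split can be rebuilt by hand from listings sorted by cohort.
- **No planned inference is affected.** A reader might infer a distorted treatment effect, for instance by positing an infusion-site event in 1 of 4 IV placebo subjects and 2 of 6 in an IV active arm, so that the excess grows when the placebo rate becomes 1 of 8. Those counts have no source in the documents, and no active-minus-placebo difference is a planned output. Infusion-site terms are also the rows where the route is most obvious, because SAP 9.1.1 tabulates by preferred term and such an event could only come from the IV subjects. The primary manogepix PK is untouched, since the PK set requires measurable manogepix.
- **A denominator of 8 is better than 4.** This is a legitimate aim in a small study. However, the plan already works with a placebo column of 4 in Part-2, and keeping the pooled column preserves the gain.

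The dosing-period argument is thin. The study is single-centre with common eligibility criteria, and the only stated gap is a minimum of 3 days. The point rests on route.

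**Conclusion.** The point holds as a minor one. The SAP departs from the protocol's by-cohort safety display for Part-1 placebo and neither declares nor justifies it. As a result, neither route is shown beside its own within-cohort placebo group in the Part-1 summary tables and figures.

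The effect is limited to descriptive, secondary safety summaries, and chiefly to rows where the route cannot be read from the label. Its size depends on how far the two placebo groups differ: none if their rates are equal, and a halving of the IV background if the event occurs only with infusion. That the routes differ at all, including any effect of the infused fluid on the 3-hour laboratory sample, is an assumption that the documents neither quantify nor exclude. The textual discrepancy is certain; its practical impact is not.

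**What to change.** In SAP Section 4, replace the single Part-1 placebo group with two, oral placebo (Cohort 1, n=4) and IV placebo (Cohort 2, n=4), each placed beside the active arms of its cohort. Keep the pooled n=8 column as supportive, and note it in Section 11 with a sentence of justification. The Section 11 entry alone would record the departure but leave the main display mixed.

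The cost is two extra columns in the Part-1 tables and the matching shells. No new data, change in conduct or protocol amendment is needed, and the change should be made before unblinding. The drawback is imprecise columns: with no events, n=4 excludes only rates above 52.7%, against 31.2% for n=8. The retained pooled column offsets this.

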- m. All subjects in PART-2 receive a loading dose of 1,000 mg fosmanogepix or placebo (3-hour IV infusion, BID) on Day 1 after 4 hours fasting followed by a maintenance dose of 600 mg or placebo (3-hour IV infusion, QD) on Days 2 and 3. Subjects in Cohort 3 will then continue to receive the IV maintenance dose administration of 600 mg fosmanogepix or placebo, QD. Subjects in Cohort 4 will switch to oral administration of 800 mg fosmanogepix or placebo, QD on Days 4 – 7. On Day 7, all subjects (Cohort 3 and Cohort 4) will receive study drug after 10 hours fasting.
- n. Blood samples for PK analysis will be taken at each time point. See the PK Sampling Schedule [below](#).

PART-2: PK sampling schedule

Study day	Day 1			Day 2, 3, 6	Day 7								Day 8		Day 9	Day 10	Day 11	Day 13	Day 17	Day 22
Hours after dose ^a (±PK sampling window)	0 ^b	3 ^d (End of first dose on Day 1)	12 ^c (Pre-dose of second dose on Day 1)	0 ^c	0 ^c	1 (±6 min)	2 (±12 min)	3 ^d	4 (±24 min)	6 (±30 min)	8 (±30 min)	12 (±1 h)	24 (±1 h)	36 (±1 h)	48 (±1 h)	72 (±1 h)	96 (±1 h)	144 (±3 h)	240 (±3 h)	360 (±3 h)
PK blood sampling	X	X	X	X	X	X	X	X	X	X	X	X	X	X	X	X	X	X	X	X

For abbreviations see the List of Abbreviations [above](#).

- The PK collection time points on Day 1 are shown in hours relative to the start of first dose administration on Day 1. The PK collection time points from Day 7 to Day 22 are shown in hours relative to the start of the last dose on Day 7. On Day 7, the PK sample should be taken after at least 10 hours of fasting.
- Pre-dose PK sample collection, 30 minutes before first dose administration (start time) on Day 1. The PK sample should be taken after at least 10 hours of fasting.
- Pre-dose PK sample collection, 30 minutes before second dose administration (start time) on Day 1, and before administration (start time) on Day 2, Day 3, Day 6, and Day 7.
- The PK sample should be collected within 5 minutes before the end of infusion (for all subjects on Day 1, and for Cohort 3 only on Day 7). For Cohort 4 on Day 7, the PK sample should be collected 3 hours (±18 minutes) after administration of the oral dose.

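### Cohorts 3 and 4 share one IV regimen until the Day 4 dose, yet the SAP plans no pooled active summary (n=16) of the early concentrations and primary troughs

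*SAP*

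**What the plan says.** **Regimen.** Protocol Section 6.1.1.2 gives the Day 1 loading schedule for Part-2: "All subjects (Cohort 3 and Cohort 4) will receive a 3-hour IV infusion (1,000 mg fosmanogepix or placebo, BID) 12 hours" apart. Footnote m of the Part-2 schedule in Protocol Section 1.3 continues for everyone: "followed by a maintenance dose of 600 mg or placebo (3-hour IV infusion, QD) on Days 2 and 3". The cohorts separate only afterwards: "Subjects in Cohort 4 will switch to oral administration of 800 mg fosmanogepix or placebo, QD on Days 4" to 7, while Cohort 3 stays on the infusion.

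**Primary troughs.** SAP Section 3.2.1 lists six time points for Ctrough: "Trough concentration) on Day 1 (second dose), Day 2, Day 3, Day 6, Day 7, Day 8 (24 hours after last dose"). The Part-2 PK sampling schedule draws the later pre-dose samples "before administration (start time) on Day 2, Day 3, Day 6, and Day 7". It also has a sample at the end of the first Day 1 infusion in all subjects.

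**Numbers and reporting groups.** "Eight subjects in each cohort will be randomized to fosmanogepix and two subjects will be randomized to placebo" (SAP Section 3.1, Part-2). SAP Section 4 then reports "Part-2: IV only, IV and oral, Placebo (pooled cohort 3 and cohort 4"). Placebo is pooled across the two cohorts and active drug is not. Protocol Section 9.3.1.2 likewise presents PK by cohort, and Section 9.3.2 pools only placebo for the Part-2 safety analysis.

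**Statistics planned.** Concentrations get a geometric mean but no geometric CV (SAP 8.1). PK parameters get both (SAP 8.2). SAP Table 2 names only Day 7 and Day 8 as the source of Ctrough and mentions the earlier pre-dose samples in a footnote as being collected. SAP Section 4.3.2 rules out reporting adverse events by visit, and no adverse event table is split by period.

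**The concern.** Until the Day 4 dose the 16 active subjects have the same drug, dose, route, infusion time and schedule. A Day 2 trough in Cohort 3 and one in Cohort 4 therefore measure the same thing, apart from any difference between the people enrolled. Two estimates on 8 subjects each are less precise than one estimate on 16.

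This matters because these troughs are primary endpoints. Protocol Section 4.3.2 also says the Part-2 regimen was chosen so that PK, safety and tolerability could be compared with non-Chinese populations. For concentrations after the loading day, that comparison is best made with every subject who received the loading day.

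**Working it through.** **Step 1. The plan's own figures.** Part-2 has no power or precision calculation to reproduce, but the counts agree. Ten per cohort at 4:1 gives 10 × 4/5 = 8 active and 10 × 1/5 = 2 placebo. Two cohorts give 2 × (8 + 2) = 20 subjects, of whom 16 are active.

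**Step 2. Which samples precede the switch.** The regimens diverge at the Day 4 dose.

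| Sample | Before the Day 4 dose? | Primary trough? |
|---|---|---|
| Day 1, end of first infusion | yes | no |
| Day 1, before second dose | yes | yes |
| Day 2, pre-dose | yes | yes |
| Day 3, pre-dose | yes | yes |
| Day 6, pre-dose | no | yes |
| Day 7, pre-dose | no | yes |
| Day 8, 24 h after last dose | no | yes |

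Three of six primary trough time points, plus the end-of-infusion concentration, fall in the common period.

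**Step 3. Precision of a mean.** The plan reports no confidence interval; one is used here only as a yardstick. Half-width in SD units is t(0.975, n−1)/√n.

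- n = 8: 2.365/2.828 = 0.836
- n = 16: 2.131/4 = 0.533
- Ratio: 0.533/0.836 = 0.637, so 36% narrower
- Standard error: 1/√8 = 0.354 SD against 1/√16 = 0.250 SD, 29% smaller

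**Step 4. Geometric mean.** The documents give no between-subject CV, so a range is assumed. With s = √ln(1 + CV²), the interval relative to the geometric mean is exp(±t·s/√n).

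| Assumed CV | s | n = 8 (fold) | n = 16 (fold) |
|---|---|---|---|
| 20% | 0.198 | 0.85-1.18 | 0.90-1.11 |
| 30% | 0.294 | 0.78-1.28 | 0.86-1.17 |
| 50% | 0.472 | 0.67-1.48 | 0.78-1.29 |

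**Step 5. What can be rebuilt from the planned tables.** The pooled mean is the average of the two cohort means (equal n). The pooled variance is [7·s₁² + 7·s₂² + 8(m₁ − m)² + 8(m₂ − m)²]/15. A numerical check on simulated data matched the direct calculation. The geometric mean can be rebuilt in the same way if no value is below the quantification limit. The median cannot. Nor can the geometric CV be taken from the concentration tables, which do not report it.

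**Step 6. Adverse events.** If no subject has a given event, the one-sided 95% upper bound on its rate is 1 − 0.05^(1/n): 1 − 0.05^(1/8) = 31% and 1 − 0.05^(1/16) = 17%. Neither bound corresponds to a planned table, since no adverse event table is restricted to Days 1-3 even within a cohort.

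**The case against.** **By-cohort reporting follows the protocol, and the trial is descriptive.** Part-2 was sized per cohort, no hypothesis is tested and no confidence interval is planned, so a narrower interval changes no decision. This stands. It makes the point one about a missing supplementary summary and not an error. Precision still matters in a descriptive study whose results are meant for comparison with other populations.

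**Same dosing does not make one sample.** Protocol Section 6.3 describes 4:1 randomisation to drug or placebo with ten subjects in each cohort. It does not say subjects are randomised between cohorts. If the cohorts differ systematically, the pooled figure averages two groups and its interval is too narrow. This also stands, and is why the pooled summary should sit beside the cohort tables and not replace them.

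**Pooled placebo is a weak precedent.** With two placebo subjects per cohort there is an obvious practical reason to pool, and placebo PK samples are not routinely analysed (Protocol Section 6.4). The case for pooling active subjects rests on their identical treatment, not on what is done with placebo.

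**Two stronger readings fail.** A reader might infer that half the data are discarded. They are not: both groups of eight are summarised, troughs are plotted by study day, and all values are listed. A reader might also infer that the SAP attributes a Day 1-3 adverse event in Cohort 4 to the oral switch. It does not. The IV-and-oral label names the assigned regimen, and event listings are planned.

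**Conclusion.** The point holds as a missed gain in precision. For the Day 1 end-of-infusion concentration and three of six primary trough time points, each planned estimate uses 8 of 16 identically treated subjects. Pooling would narrow a 95% interval by 36%, whatever the variance, provided the two cohorts can be treated as samples from one population with a common SD. The fold ranges rest further on assumed CVs of 20% to 50% and roughly log-normal concentrations.

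The Day 6, 7 and 8 troughs and the Day 7 parameters are unaffected, because the regimens differ by then and pooling would be inappropriate.

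For safety the gap is different in kind: no adverse event table by period exists, so pooling alone would not supply one. An onset cut-off would be needed too, and it would miss later-onset effects of the early infusions. The window should be called the common IV period (Days 1-3), since loading is Day 1 only. The change is worth making, but the validity of the planned analysis does not depend on it.

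**What to change.** In SAP Sections 4, 8.1 and 8.2:

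1. Keep all by-cohort tables and figures.
2. Add a pooled Cohort 3 and Cohort 4 active group (n=16) for manogepix concentrations and Ctrough from Day 1 through the Day 3 pre-dose sample, including geometric mean and geometric CV.
3. Add a note that allocation between cohorts is not stated to be random, so the pooled figures are to be read alongside the cohort figures.
4. In Table 2, state that the Day 1 (second dose), Day 2, Day 3 and Day 6 troughs are summarised as well as collected, to match the primary endpoint list in Section 3.2.1.
5. Optionally, add one pooled table of treatment-emergent adverse events with onset before the Day 4 dose, titled as the common IV period (Days 1-3).

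The cost is one extra column or table for PK and, if chosen, one for adverse events. No subjects, samples, visits or dosing change.
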